#### 4.1.3 Safety Endpoint

Both emergency and routine immunization schedules included the following safety endpoints:

- (1) Adverse events includes:
  - Solicited adverse events: the systemic adverse events and local adverse events actively collected during the solicitation period (within 0-7 days after each dose of vaccination). Systemic adverse events include fever (axillary), acute allergic reaction, skin and mucosa abnormality, diarrhea, anorexia, vomiting, nausea, muscle pain, headache, cough, fatigue; local adverse events includes pain, induration, swelling, redness, rash, and pruritus.
  - Unsolicited adverse events: Including other adverse events in the solicitation period and all adverse events in the unsolicitation period.
- (2) Serious adverse event (SAE):
- (3) Laboratory testing, includes:
  - Blood routine: Leukocyte count, hemoglobin, platelet count;
  - Blood biochemical: Alanine aminotransferase (ALT), aspartate aminotransferase (AST), total bilirubin (TBIL), creatinine (CR), creatine phosphokinase (CPK);
  - Urine routine: Urine protein (pro), urine sugar, urine red blood cell.
- (4) Inflammatory factor: IL-6, IL-2, and TNF- $\alpha$  in serum.
- (5) Antinuclear antibody: The positive rates at 7, 14, 21, 28, 42 days after the first dose of vaccination (emergency immunization schedule) and 28, 35, 42, 56 days after the first dose of vaccination (routine immunization schedule).

## 4.2 Endpoint of Phase II

### 4.2.1 Immunogenicity Endpoint

#### 4.2.1.1 Primary Endpoint

The main immunogenicity endpoints of emergency immunization schedule and routine immunization schedule were defined as follows:

- Emergency immunization schedule: the seroconversion rate-1 at 14 days after the whole schedule vaccination;
- Emergency immunization schedule: the seroconversion rate-2 at 14 days after the whole schedule vaccination;
- Routine immunization schedule: the seroconversion rate-1 at 28 days after the whole schedule vaccination;
- Routine immunization schedule: the seroconversion rate-2 at 28 days after the whole schedule vaccination.

#### 4.2.1.2 Secondary Endpoint

The emergency immunization schedule at 14 days after the whole schedule vaccination and the routine immunization schedule at 28 days after the whole schedule vaccination are defined as the following secondary immunogenicity endpoint:

- (1) Post-immunization neutralization antibody  $\geq 4$  rate;
- (2) Post-immunization neutralizing antibody titer  $\geq 4$  in the subjects with pre-immunization  $< 4$ ;
- (3) The 4-time increase rate of neutralizing antibody after immunization in the subjects  $\geq 4$  before immunization;
- (4) Post-immunization neutralization antibody  $\geq 8$  rate;
- (5) Post-immunization neutralizing antibody titer  $\geq 8$  in the subjects with pre-immunization  $< 8$ ;
- (6) The 4-time increase rate of neutralizing antibody after immunization in the subjects  $\geq 8$  before immunization;
- (7) Post-immunization neutralizing antibody GMT and GMI;
- (8) Post-immunization neutralizing antibody GMT and GMI in the subjects with pre-immunization  $< 4$ ;
- (9) Post-immunization neutralizing antibody GMT and GMI in the subjects with post-immunization  $\geq 4$ ;
- (10) Post-immunization neutralizing antibody GMT and GMI in the subjects with pre-immunization  $< 8$ ;
- (11) Post-immunization neutralizing antibody GMT and GMI in the subjects with post-immunization  $\geq 8$ ;

The emergency immunization schedule at 28 days after the whole schedule vaccination is defined as the following secondary immunogenicity endpoint:

- (12) The neutralization antibody at 28 days after the whole schedule vaccination  $\geq 4$  rate;
- (13) The neutralizing antibody at 28 days after the whole schedule vaccination  $\geq 4$  rate in the subjects with pre-immunization  $< 4$ ;
- (14) The 4-time increase rate of neutralizing antibody at 28 days after the whole schedule vaccination in the subjects  $\geq 4$  before immunization;
- (15) The seroconversion rate-1 at 28 days after the whole schedule vaccination
- (16) The neutralization antibody  $\geq 8$  rate at 28 days after the whole schedule vaccination;
- (17) The neutralizing antibody at 28 days after the whole schedule vaccination  $\geq 8$  in the subjects with pre-immunization  $< 8$ ;
- (18) The 4-time increase rate of neutralizing antibody at 28 days after the whole schedule vaccination in the subjects  $\geq 8$  before immunization;
- (19) The seroconversion rate-2 at 28 days after the whole schedule vaccination
- (20) The neutralizing antibody GMT and GMI at 28 days after the whole schedule vaccination;
- (21) The neutralizing antibody GMT and GMI at 28 days after the whole schedule vaccination in the subjects with pre-immunization  $< 4$ ;
- (22) The neutralizing antibody GMT and GMI at 28 days after the whole schedule vaccination in the subjects with

post-immunization  $\geq 4$ ;

- (23) The neutralizing antibody GMT and GMI at 28 days after the whole schedule vaccination in the subjects with pre-immunization  $< 8$ ;
- (24) The neutralizing antibody GMT and GMI at 28 days after the whole schedule vaccination in the subjects with post-immunization  $\geq 8$ ;

#### 4.2.2 Exploratory Endpoint

The exploratory endpoints of emergency immunization schedule and routine immunization schedule were defined as follows:

- (1) Neutralization antibody  $\geq 4$  rate at 6 months after the whole schedule vaccination
- (2) Neutralization antibody  $\geq 8$  rate at 6 months after the whole schedule vaccination
- (3) GMT of neutralizing antibody at 6 months after the whole schedule vaccination

#### 4.2.3 Safety Endpoint

The safety endpoints of emergency immunization schedule and routine immunization schedule were as follows:

- (1) Adverse events includes:
  - Solicited adverse events: the systemic adverse events and local adverse events actively collected during the solicitation period (within 0-7 days after each dose of vaccination). Systemic adverse events include fever (axillary), acute allergic reaction, skin and mucosa abnormality, diarrhea, anorexia, vomiting, nausea, muscle pain, headache, cough, fatigue; local adverse events includes pain, induration, swelling, redness, rash, and pruritus.
  - Unsolicited adverse events: Including other adverse events in the solicitation period and all adverse events in the unsolicitation period.
- (2) Serious adverse event (SAE);
- (3) Antinuclear antibody: The positive rates at 28, 42 days after the first dose of vaccination (emergency immunization schedule), and 56 days after the first dose of vaccination (routine immunization schedule). Positive was defined as antinuclear antibody concentration  $\geq 10\text{U/ml}$ .

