**Table 1 Blood and urine collection at each time point in safety observation**

Phase and immunization schedule	Sample type	Test contents	Sampling time
Phase I - emergency immunization schedule	Blood	Blood Routine, Blood Chemistry	Before the first dose of inoculation (D-7~D0), 3 days after the first dose of inoculation (D3), before the second dose inoculation (D14), 3 days after the second dose of inoculation (D17)
		Inflammatory Factor	Before the first dose of inoculation (D0), 7 days after the first dose of inoculation (D7), before the second dose inoculation (D14), 7 days after the second dose of inoculation (D21)
		Antinuclear Antibody	Before the first dose of inoculation (D0), 7 days after the first dose of inoculation (D7), 14 days after the first dose of inoculation (D14), 21 days after the first dose of inoculation (D21), 28 days after the first dose of inoculation (D28), 42 days after the first dose of inoculation (D42), 6 months after the whole schedule vaccination (D194)
Phase I - routine immunization schedule	Urine	Urine Routine	Before the first dose of inoculation (D-7~D0), 3 days after the first dose of inoculation (D3), before the second dose inoculation (D14), 3 days after the second dose of inoculation (D17)
	Blood	Blood Routine, Blood Chemistry	Before the first dose of inoculation (D-7~D0), 3 days after the first dose of inoculation (D3), before the second dose inoculation (D28), 3 days after the second dose of inoculation (D31)
		Inflammatory Factor	Before the first dose of inoculation (D0), 7 days after the first dose of inoculation (D7), before the second dose inoculation (D28), 7 days after the second dose of inoculation (D35)
		Antinuclear Antibody	Before the first dose of inoculation (D0), 28 days after the first dose of inoculation (D28), 35 days after the first dose of inoculation (D35), 42 days after the first dose of inoculation (D42), 56 days after the first dose of inoculation (D56), 6 months after the whole schedule vaccination (D208)
Urine	Urine Routine	Before the first dose of inoculation (D-7~D0), 3 days after the first dose of inoculation (D3), before the second dose inoculation (D28), 3 days after the second dose of inoculation (D31)	
Phase II - emergency immunization schedule	Blood	Antinuclear Antibody	Before the first dose of inoculation (D0), 28 days after the first dose of inoculation (D28), 42 days after the first dose of inoculation (D42), 6 months after the whole schedule vaccination (D194)

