Phase II - routine immunization schedule	Blood	Antinuclear Antibody	Before the first dose of inoculation (D0), 28 days after the whole schedule vaccination (D56), 6 months after the whole schedule vaccination (D208)

Immunogenicity observation: blood samples were collected from all subjects at different time points before and after immunization for the detection of serum neutralizing antibodies. In phase I, IgG, IgM antibodies, and specific T cell response assay (IFN- $\gamma$  detection using Elispot method) were also required. In the immunogenicity observation, the blood collection at each time point is shown in Table 2.

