The positive rate of antinuclear antibody was calculated by group on the 28th day after the first dose of immunization in phase II emergency immunization schedule, and their confidence intervals will be estimated by the Clopper-Pearson method. A Chi-square test or Fisher exact test will be used to detect differences among groups. Furthermore, if statistically significance exists, the pairwise comparison will be conducted between groups by Chi-square test or Fisher exact test.

Descriptive statistics in each group for the antinuclear antibody geometric mean titers (GMTs) and geometric mean increases (GMIs) at 7th day after the first dose of immunization in phase II emergency immunization schedule, including geometric mean and 95% confidence interval (95% CI), will be provided by group. ANOVA model with log-transformation (per GMT and GMI as above) will be used to detect the difference among groups.

The statistical analysis method of antinuclear antibody evaluation on 42 days after the first dose immunization of phase II emergency immunization schedule and 56 days after the first dose immunization of phase II routine immunization schedule was the same as that of 28 days after the first dose in emergency immunization schedule of phase II.

Chi-square test or Fisher exact test will be used to detect differences of positive rate of antinuclear antibody between the middle dose group and the high-dose group at 28 days after the whole immunization in phase II. Additionally, using the same method, the positive rate of antinuclear antibody comparison between emergency immunization schedule and routine immunization schedule in Phase II will be conducted by group (medium-dose group and high-dose group) at 14 days and 28 days after the whole schedule vaccination, respectively. 14 days after the whole schedule vaccination is 28 days after their first dose in emergency immunization schedule and 42 days after the first dose in routine immunization schedule, respectively.

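### The 6-month ANA safety samples have no planned endpoint or analysis, and the ANA positive rate does not separate new from pre-existing positivity.

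*SAP*

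**What the plan says.** **Sampling.** Table 1 (SAP section 3.1) lists ANA among the safety samples. All four phase-by-schedule rows include D0 and a 6-month draw. The emergency rows end with "42 days after the first dose of inoculation (D42), 6 months after the whole schedule vaccination (D194"). The Phase II routine row reads "Before the first dose of inoculation (D0), 28 days after the whole schedule vaccination (D56), 6 months after the whole schedule vaccination (D208"), and the Phase I routine row also ends at D208.

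**Endpoints.** Section 4.1.3(5), Phase I: "Antinuclear antibody: The positive rates at 7, 14, 21, 28, 42 days after the first dose of vaccination" for the emergency schedule, and days 28, 35, 42 and 56 for the routine schedule. Section 4.2.3(3), Phase II: "Antinuclear antibody: The positive rates at 28, 42 days after the first dose of vaccination (emergency immunization schedule), and 56 days after" the first dose for the routine schedule. Section 4.2.3 also sets the cut-off: "Positive was defined as antinuclear antibody concentration" of at least 10 U/ml, with no reference to the D0 value. Section 4.1.3 gives no cut-off for Phase I.

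**Analysis.** For Phase II, section 6.6.3 starts from "The positive rate of antinuclear antibody was calculated by group on the 28th day after the first dose of immunization" and extends the method to D42 (emergency) and D56 (routine). For Phase I it covers the same visits as 4.1.3(5). It tests positive rates among groups and between schedules. It also plans ANA geometric mean titre and GMI with a log-scale ANOVA. For Phase II, the visit named for GMT and GMI is day 7 of the emergency schedule.

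**The concern.** There are two linked gaps.

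First, a safety sample is scheduled for every subject at 6 months and then given no endpoint, method or comparison. It is the only ANA sample taken later than 28 days after the second dose. If the plan is followed literally, those results are never summarised by group.

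Second, the natural question for an autoantibody safety marker is how many subjects who were negative before vaccination became positive afterwards. A plain positive rate mixes them with subjects who were positive at D0. The SAP handles baseline differently elsewhere: neutralising-antibody seroconversion (section 4.1.1) is conditioned on the pre-vaccination titre, and Phase I laboratory parameters (section 6.6.2) get change from baseline and shift tables. ANA gets neither a new-positivity rate nor a shift table, although the D0 sample exists.

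**Working it through.** **Step 1. Are the 6-month draws distinct planned visits?** Second doses fall on D14 and D28. 194 − 14 = 180 and 208 − 28 = 180. Both are 6 months after the second dose, so they do not duplicate D42 or D56.

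**Step 2. Sampled against analysed (ANA only).**

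| Phase, schedule | Sampled after D0 (Table 1) | Positive rate planned (4.1.3, 4.2.3, 6.6.3) | Sampled, not analysed |
|---|---|---|---|
| I, emergency | D7, 14, 21, 28, 42, 194 | D7, 14, 21, 28, 42 | D194 |
| I, routine | D28, 35, 42, 56, 208 | D28, 35, 42, 56 | D208 |
| II, emergency | D28, 42, 194 | D28, 42 | D194 |
| II, routine | D56, 208 | D56 | D208 |

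The other 6-month material does not fill the gap. Sections 4.1.2 and 4.2.2 and the 6-month parts of 6.5 concern neutralising antibody, and the Immune Persistence Set in section 5 is defined by antibody titre.

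**Step 3. Where does D0 enter?** Only through GMI, which is an increase over baseline. It is a group mean on the log scale and does not say how many subjects crossed the cut-off. In Phase I it is planned at each listed visit. In Phase II it is written for day 7, but the Phase II rows of Table 1 have no day-7 ANA sample, so as printed it cannot be computed. The neighbouring paragraphs refer to D28, D42 and D56, which suggests that D28 was meant.

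**Step 4. Group sizes.** The SAP's figures reproduce: 600 × (2, 2, 1)/5 = 240, 240, 120. Per schedule: 300 × (2, 2, 1)/5 = 120, 120, 60. A planned pairwise vaccine-placebo comparison within a schedule is therefore 120 vs 60.

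**Step 5. Size of the dilution (illustration only).** The SAP gives no ANA rates, so these are assumptions. Let *b* be the share positive at D0 and *i* the new positivity among D0-negatives, with every D0-positive subject staying positive. Then raw rate = *b* + (1 − *b*) × *i*.

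For *b* = 10% and *i* = 6% vs 1%:
- vaccine: 0.10 + 0.90 × 0.06 = 15.4%
- placebo: 0.10 + 0.90 × 0.01 = 10.9%
- raw ratio 15.4/10.9 = 1.4, against 6/1 = 6.0 for new positivity
- raw difference 4.5 points, against 5.0

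Exact power of the two-sided 5% Fisher test, 120 vs 60 for the raw rate and D0-negatives only for new positivity (120 and 60 each times 1 − *b*):

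| *b* | Raw ratio (6% vs 1%) | Power raw / new (6% vs 1%) | Raw ratio (10% vs 1%) | Power raw / new (10% vs 1%) |
|---|---|---|---|---|
| 0% | 6.0 | 17% / 17% | 10.0 | 63% / 63% |
| 5% | 1.8 | 12.0% / 14.5% | 2.4 | 33% / 58% |
| 10% | 1.4 | 9% / 12% | 1.7 | 24% / 54% |
| 20% | 1.2 | 7% / 8% | 1.35 | 16% / 44% |

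The dilution is nil if nobody is positive at D0. In power terms it is small at 6% vs 1% and substantial only if the true effect is larger.

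**The case against.** **Baseline is not ignored.** A reader might infer that the plan disregards the D0 sample. It does not: ANA GMI uses it. What stands is narrower: GMI counts no new positives, and its Phase II date cannot be right as printed.

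**The comparison is not biased.** Within a schedule, randomisation makes the raw-rate contrast between groups unbiased, and chance imbalance at D0 is not a planning error. The cost is dilution. This defence is weaker for the between-schedule comparisons in 6.6.3, because the SAP describes randomisation only within each schedule (sections 3.1 and 3.2.1).

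**A large loss of power is not shown.** Pooling all Phase II vaccinees against all placebo recipients (480 vs 120) at 10% background and 6% vs 1% gives about 21% raw against 63% for new positivity. The SAP plans no such pooled test. The size also depends on scale: the ratio shrinks sharply, the risk difference by only half a point. Section 6.7 makes p-values nominal, so lost power changes no decision rule, although the descriptive ratio is diluted all the same.

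**The 6-month gap may be less serious than it sounds.** SAEs are collected to 6 months (section 3.1), and the table shells sit in a separate appendix that is not shown (section 7). A reader might infer that late autoimmunity would go undetected; nothing in the SAP establishes that. It remains that no endpoint or method in the SAP text covers ANA at D194 or D208.

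**Conclusion.** The concern holds on two counts. The firmer one needs no assumption: ANA at D194 and D208 is collected as a safety measurement in both phases and both schedules, and no endpoint or analysis in the SAP uses it.

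The second is a weakness of definition. The positive-rate endpoint does not distinguish new from pre-existing positivity, the only baseline-adjusted ANA measure does not count new positives, and for Phase II that measure is tied to an unsampled day. The effect is loss of sensitivity, not bias within a schedule. Its size is unknown because the SAP states no ANA rates. In the planned 120 vs 60 comparison it is about 3 percentage points of power at 10% background and 6% vs 1% new positivity, and about 30 points if new positivity is 10% vs 1%. The primary immunogenicity endpoints are untouched. The change should be made because it is cheap and makes the safety report complete.

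**What to change.** 1. Add D194 (emergency) and D208 (routine) to the ANA endpoint in 4.1.3(5) and 4.2.3(3) and to the analysis in 6.6.3, for both phases.
2. Alongside the raw positive rate, report by group and visit the proportion newly positive among D0-negative subjects, with a shift table from D0 to each visit. Keep the raw rate.
3. State whether the 10 U/ml cut-off given for Phase II also applies to Phase I, or give the Phase I cut-off. New positivity in Phase I cannot be defined without it.
4. In 6.6.3, change the Phase II ANA GMT/GMI visit from day 7 to one that Table 1 samples. D28 would match the positive-rate paragraph before it.

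**Cost.** SAP wording and one or two more tables; every sample is already planned. Subjects positive at D0 leave the denominator of the new-positivity rate, so that rate rests on fewer subjects: 108 vs 54 instead of 120 vs 60 at an assumed 10% background.

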### 5. Analysis Set

**Full Analysis Set (FAS):** A subjects defined according to the principle of intent analysis (ITT), including all the subjects who have been randomized, have received at least one dose of vaccination, have finished blood collection before/after vaccination for at least one time with the corresponding antibody assay results provided. The subjects who are vaccinated with the wrong vaccine will be kept in the originally assigned group according to the ITT principle, for the immunogenicity evaluation.

**Per-Protocol Set (PPS):** A subset of FAS, including all the subjects who meet the inclusion criteria and don't meet the exclusion criteria, have been randomized, have finished the full-course vaccination within the protocol required time window, and have finished the blood collection before/after vaccination with the corresponding antibody assay results provided. Subjects who meet the following conditions are not allowed to enter PPS:

- (1) Those who violate the test scheme;
- (2) Those who are vaccinated with the wrong vaccine;
- (3) Use of protocol prohibited vaccines or drugs:
  - Other investigational or unlicensed products (drugs or vaccines)
  - long-term use (lasting more than 14 days) of immunosuppressive or other immunomodulatory drugs (inhaled or topical steroids are allowed)

- Immunoglobulin and/or blood preparations
- (4) Newly diagnosed autoimmune diseases, including human immunodeficiency virus (HIV) infection;
- (5) Other situations affecting the evaluation of vaccine immunogenicity.

**Immune Persistence Set (IPS):** All subjects who had completed the whole schedule vaccination and had effective antibody titer value at 6 months after the whole schedule vaccination were included.

The above Full Analysis Set, Per-Protocol Set, and Immune Persistence Set are defined for emergency immunization schedule and routine immunization schedule in phases I and II.

**Safety Analysis Set (Safety Set, SS):** All randomized subjects with at least one dose of the study vaccine were included. Among them, according to ASaT (All Subjects as Treated) principle, the safety evaluation was carried out according to the actual vaccination group.

- The safety set is mainly used for the safety evaluation of the vaccine, and the safety set of each dose is used for the safety evaluation of each dose.
- The safety set is divided into total safety set, first dose safety set, and second dose safety set. The safety analysis of each dose was based on the actual number of vaccinated people. The first dose of safety set includes all subjects who have completed the first dose of vaccination, which are recorded as SS1; the second dose of safety set includes all subjects who have completed the second dose of vaccination and are recorded as SS2.

The above analysis sets will be discussed and decided by the main researcher, the sponsor, the statistician, and the data manager before the database is locked and in the data blind audit process.

## 6. Statistical Analysis Method

### 6.1 General Principles

Quantitative data will be summarised descriptively, including mean, median, standard deviation, minimum, and maximum. The categorical data or ordinal data will be summarised by count and proportion.

All statistical analysis will conduct with SAS 9.4.

### 6.2 Enrollment and completion

The number of subjects screened, randomized, complete, and enter the analysis subjects will be provided by group per phase and immunization schedule. The reasons to discontinue from the study will be summarised. The subjects, who screen failure, discontinue from the study and excluded from the analysis subjects, will be listed respectively.

